#### Session Measures:

1) Minnesota Nicotine Withdrawal Symptom Checklist (M-NWSC): Smokers will be asked to rate several nicotine withdrawal symptoms from on a 100 mm scale, "not at all" to "extremely." The items are derived from the M-NWSC (Hughes and Hatsukami 1986) and have been used in previous human laboratory studies (Eissenberg et al. 1996). The items include cigarette craving, irritability/anger, anxiety/tension, difficulty concentrating, restlessness, increased appetite, depressed mood, and insomnia.

2) Positive and Negative Affect Schedule (PANAS): The PANAS is a 20-item scale that assesses both negative and positive affective states (Watson et al. 1988). This scale is sensitive to the affective symptoms of tobacco withdrawal and predicts relapse to smoking (Kenford et al. 2002).

3) Brief Questionnaire on Smoking Urges (BQSU): This 10-item scale has been found to be highly reliable and reflects levels of nicotine deprivation (Bell et al. 1999; Morgan et al. 1999). This scale will be used to monitor cigarette craving.

4) Drug Effects Questionnaire (DEQ): Smokers will rate 5 items that are related to nicotine effect on a 100 mm scale, "not at all" to "extremely." The items are feeling the "drug strength," feel "good" drug effects, feel "bad" drug effects, liking the drug effects, and "head rush." This instrument allows rapid detection of nicotine effects and is adapted from a VAS (Soria et al. 1996).

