75 Min	26	HR/BP, DEQ IV sampling Option 4
76 Min	27	HR/BP DEQ
77 Min	28	HR/BP,
78 Min	29	HR/BP, DEQ
80 Min	30	HR/BP, DEQ
90 Min	31	HR/BP, DEQ IV sampling Option 5

91 Min	32	HR/BP DEQ
92 Min	33	HR/BP,
93 Min	34	HR/BP, DEQ
95 Min	35	HR/BP, DEQ
105 Min	36	HR/BP, DEQ IV sampling Option 6
106Min	37	HR/BP DEQ
107Min	38	HR/BP,
108 Min	39	HR/BP, DEQ
110 Min	40	HR/BP, DEQ
120 Min	41	HR/BP DEQ IV sampling Option 7
121 Min	42	HR/BP DEQ
122 Min	43	HR/BP,
123 Min	44	HR/BP, DEQ
125 Min	45	HR/BP, DEQ
135 Min	46	HR/BP DEQ IV sampling Option 8
136 Min	47	HR/BP DEQ
137 Min	48	HR/BP,
138 Min	49	HR/BP, DEQ
140 Min	50	HR/BP, DEQ
150 Min	51	HR/BP DEQ IV sampling Option 9
151 Min	52	HR/BP DEQ
152 Min	53	HR/BP,
153 Min	54	HR/BP, DEQ
155 Min	55	HR/BP, DEQ
165 Min	56	HR/BP DEQ IV sampling Option 10
166 Min	57	HR/BP DEQ
167 Min	58	HR/BP,
168 Min	59	HR/BP, DEQ
170 Min	60	HR/BP, DEQ
180-240 Min	61	HR/BP, DEQ, EKG, SCF M-NWSC, BQSU, PANAS, SNACK and Discharge

\*Same measure will be obtained following saline and each nicotine administration. For brevity, only the measures after saline are shown.

Abbreviations: CO: Alveolar carbon monoxide, HR/BP: Heart rate/Blood pressure; EKG: Electrocardiogram; SCF: Symptom Checklist form; M-NWSC: Minnesota Nicotine Withdrawal Symptom Checklist; BQSU: Brief Questionnaire of Smoking Urges; PANAS: Positive and Negative Affective Schedule; DEQ: Drug Effects Questionnaire.

Experimental sessions: The schedule of events during the experimental sessions is shown in Table 1. Before the session begins, subjects will have an IV catheter placed and the baseline measures will be taken. Subjects will begin NSA as described below.

Nicotine self-administration procedure:

Apparatus: Saline and nicotine will be administered with two separate infusion pumps, which will be prepared with IV infusion bags randomly labeled as Drug A or B by the research pharmacist. Both the researchers and the subjects will be blind to the randomization. The infusion pumps will deliver saline and nicotine at a precise rate and volume.

Procedure: The NSA procedure will consist of two phases: Sampling and Nicotine Choice.

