We expect to observe a significant dose effect and will compare the proportion of NSAs at each dose to 0.5 across subject groups. The lowest nicotine dose that has a significantly higher proportion of NSA than 0.5 will be selected as the threshold dose (Hypothesis 1A). To assess the dose-response relationship in the preference for nicotine, polynomial effects of dose (linear, quadratic, cubic) and change-point linear models will be tested in the mixed effects logistic regression model. We anticipate that there will be a significant linear relationship between dose and response rate at lower doses with flattening of the relationship at higher doses. We will use the slope of the dose effect to assess the linear dose effect. Alternative non-linear dose response relationships will be considered if residual plots reveal significant deviations of the models from linearity. Gender differences in the shape of the curve for NSA will be examined in the logistic regression model by including gender main effect and its interactions with dose (Hypothesis 1B). Significant interactions between the group factors and dose will be considered supportive of systematic group differences in the dose-response relationships between groups. If significant interactions are observed, then separate thresholds and curves will be estimated within each subject group.

**Specific Aim #2:** To assess the threshold and dose-effect curve for the positive and negative/aversive subjective effects of IV nicotine at low doses and its relationship to nicotine reinforcement. Hypothesis #2 A: The threshold for the positive effects will be between 0.0125 to 0.1 mg/70 kg, for the negative/aversive effect it will be  $\geq 0.1$  mg/70 kg. Hypothesis #2B: Nicotine reinforcement will be positively correlated with the positive and negatively correlated with the negative/aversive subjective effects of IV nicotine.

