**Aim 2 Analysis:** The subjective-positive effects of nicotine which will be determined by the main dependent variables of scores on the "like the drug" and "want more drug" items of the Drug Effects Questionnaire, ranging from 0 to 100. The negative aversive effects of nicotine will be determined by the "dislike the drug" and "lightheaded/dizzy" item of the DEQ. The analysis for Specific Aim #2A will be similar to the analysis described for Specific Aim #1A except that the dependent variables will be continuous and thus we will use random effects linear regression. Gender effects will be explored also as outlined for Specific Aim #1B. Prior to analysis, we will also assess the distribution of the DEQ items and apply transformations as necessary. Furthermore, the mean ratings at each dose will be compared to 0. To assess the

relationship between nicotine reinforcement and positive subjective effects, and between nicotine reinforcement and negative subjective effects (Specific Aim #2B), we will use mixed effects models with the proportion of NSAs per session as the dependent variable, positive (negative) subjective effects in response to the sample dose as the main predictor of interest (in separate models for positive and negative effects). Nicotine dose, gender and the interactions among subjective effects, dose and gender will also be assessed. Non-significant interactions will be dropped from the models via backward elimination subject to the constraint that the models will be hierarchically well-formulated at each step. Statistically significant associations between subjective effects and NSA across doses and gender are expected but we will also explore whether these relationships vary by gender and dose.

**Exploratory Aim #1:** To examine the association between baseline 3HC/cotinine ratio and nicotine reinforcement threshold. To test this hypothesis, correlation analysis including 3 HC/cotinine ratio and nicotine reinforcement threshold will be performed in the total sample as well as in subgroups (male vs. female smokers).

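### Three of the four DEQ items named as Aim 2 outcomes, including both negative/aversive ones, are not on the protocol's own list of DEQ items

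*Combined protocol and SAP*

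**What the plan says.** Section 11.C (Session Measures) describes the DEQ as a short instrument: "Smokers will rate 5 items that are related to nicotine effect on a 100 mm scale". It then names the items: "The items are feeling the 'drug strength,' feel 'good' drug effects, feel 'bad' drug effects, liking the drug effects, and 'head rush". Five are announced and five are named.

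Section 12 (Aim 2 Analysis) defines the Aim 2 dependent variables as DEQ items. Positive effects are scored on the "like the drug' and 'want more drug' items of the Drug Effects Questionnaire". Negative/aversive effects "will be determined by the 'dislike the drug' and 'lightheaded/dizzy' item of the DEQ". The same items carry Hypothesis 2B: "Nicotine reinforcement will be positively correlated with the positive and negatively correlated with the negative/aversive subjective effects of IV nicotine". To test it, the plan models the proportion of nicotine choices with "subjective effects in response to the sample dose as the main predictor of interest", in separate models for positive and negative effects.

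Section 12 (Rationale for sample size) states the Aim 2 detectable effect, d' = 0.34 with 72 subjects, for two items: good effects and drug liking.

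**The concern.** The measures section and the analysis section describe two different questionnaires under one name. An outcome that is not on the form cannot be analysed, and a rating that was not asked for during a session cannot be recovered afterwards. If the five-item list is what subjects complete, the negative/aversive side of Aim 2 has no named outcome in the data. That side covers the aversive threshold in Hypothesis 2A (at or above 0.1 mg/70 kg) and the negative correlation in Hypothesis 2B. The team would have to pick substitutes from bad effects, head rush, good effects and strength without prior specification. Head rush is the awkward case, because nothing in the plan says whether it counts as pleasant or aversive.

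**Working it through.** **Step 1: match the lists.** Inputs are the DEQ item list (section 11.C), the Aim 2 outcomes (section 12, Aim 2 Analysis) and the items in the power statement (section 12, Rationale for sample size).

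| Aim 2 outcome (section 12) | Role | On the five-item DEQ list (section 11.C)? |
|---|---|---|
| like the drug | positive | yes (liking) |
| want more drug | positive | no |
| dislike the drug | negative | no |
| lightheaded/dizzy | negative | no |

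Not listed as collected: 3 of 4 overall, 1 of 2 positive, 2 of 2 negative. For Hypothesis 2B, the negative model therefore has 0 of its 2 named predictors on the list and the positive model has 1 of 2.

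**Step 2: allow generous paraphrase.** Suppose *dislike* means bad effects and *lightheaded/dizzy* means head rush. This is an assumption that no passage supports. Then 1 of 4 (*want more drug*) is still unmatched. The range is 1 of 4 to 3 of 4, and it does not reach zero.

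**Step 3: look for the items on another form.**

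- The withdrawal checklist is described in section 11.C: "The items include cigarette craving, irritability/anger, anxiety/tension, difficulty concentrating, restlessness, increased appetite, depressed mood, and insomnia". None of these eight matches the three missing items.
- In Table 1 (section 11.E), the 1 to 30 min rows run from just after the first sample infusion to the first choice, which is the period that Hypothesis 2B needs. Ten time points fall there (1, 2, 3, 5, 15, 16, 17, 18, 20 and 30 min). The DEQ is scheduled at 8 of them, the 2 and 17 min rows have only heart rate and blood pressure, and no other self-report form appears.
- The Symptom Checklist form, whose items are not described, can be read only in the 180-240 min row: "HR/BP, DEQ, EKG, SCF M-NWSC, BQSU, PANAS, SNACK and Discharge". That is after all ten choices. The 0 min row is cut off in the copy available, but ratings taken before the first infusion could not be a response to it.

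The sample-dose predictor can therefore come only from the DEQ.

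**Step 4: compare the power statement.** Its two items, good effects and drug liking, are both on the five-item list, but only liking is an Aim 2 outcome (1 of 2).

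**Step 5: reproduce the one figure attached to these outcomes.** For a one-sample test with n = 72, two-sided alpha 0.05 and 80% power:

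- Normal approximation: d = (1.960 + 0.842)/√72 = 2.802/8.485 = 0.330.
- t-test: d = 0.335.
- At d = 0.34, t-test power with n = 72 is 81.2%, and 80% power needs n = 70.

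The stated 0.34 reproduces. It is a standardized effect, so it does not depend on which item is analysed.

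**The case against.** The strongest reply is that the form itself is not in the documents and section 11.C may simply describe it incompletely. Section 12 says outright that all four items belong to the DEQ. Study 2 of the preliminary studies reports ratings of wanting more drug, and section 10 shows that the design was revised, so a stale item list is plausible. In that case the repair is a correction to one list and no analysis is lost. This stands as a possibility, and it is why the loss of the hypotheses is stated conditionally. It does not remove the contradiction: the section 11.C list is closed and agrees with its own count, and Study 2 was a different study.

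A second reply is that the matching is uneven, since *like* is allowed to equal liking but *dislike* is not allowed to equal bad effects. That is fair as far as it goes, and it gives the lower end of the range. But *want more drug* has no counterpart on any reading, and head rush is not clearly aversive.

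Third, the main outcomes are the self-administration threshold and slope. Section 4 lists self-report effects as additional measures, and good, bad and liking ratings would be available after the sample doses in any case. That is correct. It limits the damage to Aim 2 and means that both constructs could still be studied, though not on the outcomes the plan names. Nor is the mismatch in the power statement more than one of labels.

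**Conclusion.** The concern holds. As written, 3 of the 4 Aim 2 outcome items are absent from the protocol's description of the instrument said to collect them, including both negative/aversive items. Under the most generous paraphrase the count is 1 of 4.

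The consequence depends on the form. If section 11.C is accurate, the negative/aversive parts of Hypotheses 2A and 2B have no named outcome or predictor in the data, and the positive parts have liking alone. If section 12 is accurate, the item list and the count of five in section 11.C are wrong and no data are lost. Confidence is high that the two sections disagree; which one is wrong cannot be told from the documents. Aim 1, the sample size and the d' of 0.34 do not change. This should be fixed.

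**What to change.** Start by checking the DEQ form that subjects actually complete.

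1. If it contains all four Aim 2 items, correct the item list and the count of five in section 11.C.
2. If it lacks any of them, there are two routes. If sessions under the new design have not started, add the missing items to the form. Otherwise, before unblinding, redefine the Aim 2 outcomes in section 12 on items that are collected. One example is good effects and liking as positive and bad effects as negative, with the role of head rush stated in advance. The choice of constructs is the investigators' to make.

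Either way, every Aim 2 outcome in section 12 should appear in the section 11.C list, and the items in the power statement should be Aim 2 outcomes. The three lists need not be identical.

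The cost is a check of the form and a wording change in section 11.C or section 12, with a label change in the power statement if needed. Adding items also needs a form revision before sessions begin. Redefining the outcomes on collected items needs no new data.

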### Preliminary Studies

#### Study 1: Sex differences in nicotine self-administration of low doses of nicotine in smokers.

**Aim:** The goal of this study was to investigate the dose-response function for the reinforcing and subjective effects of intravenous (IV) nicotine in male and female smokers using nicotine doses that are estimated to be delivered by smoking one or two puffs of cigarettes.

**Method:** Twenty-six smokers (12 male and 14 female) participated in a double-blind, placebo-controlled, crossover study that included 4 experimental sessions. In each session, participants were randomly assigned to one of 4 doses of nicotine (0.1, 0.2, 0.3 or 0.4 mg). In each session, subjects first received the sample infusions of the assigned nicotine dose and placebo and then had the opportunity to choose between nicotine and placebo for a total of 6 choices spaced evenly over a 90-minute period. The main outcome measures were the number of nicotine choices, self-report drug effects and physiological responses. **Results:** A sex-by-dose interaction was observed in the nicotine choice paradigm (Fig 1). Nicotine self-administration rate was negatively correlated with nicotine dose in males (males displayed choice preference for low doses of nicotine over high doses of nicotine), but no significant relationship between dose and choice preference was evident in females. Overall, the number of nicotine choices was not greater than saline choices ( $p>0.05$ ).

[figure not shown]
[figure not shown]

Figure 1. The mean ( $\pm$  SEM) nicotine infusion number (maximum 6) for male (n=12) and female (n=14) subjects at each dose is shown. Nicotine self-administration frequency was negatively correlated with nicotine dose among males but not females (dose by sex  $p < 0.05$ ). Post hoc comparisons showed that both 0.1 and 0.2 mg doses were self-administered more than the 0.4 mg nicotine doses.

(0.1, 0.2, 0.3, 0.4 mg) were rated as more pleasurable than saline (Figure 2). The aversive effects were significantly higher relative to saline in response to nicotine at 0.3 mg, but not at the other nicotine doses.

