**Study 2: Higher 3-hydroxycotinine (3-HC)/cotinine is associated with greater reward and heart rate increases from intravenous nicotine:** In previous studies, high nicotine metabolite ratio (3-HC/cotinine) predicted poor outcomes for smoking cessation treatment with nicotine patch. The underlying mechanisms that associate metabolite ratio with treatment outcomes have not been fully elucidated. A total of 100 smokers were divided into quartiles based on their baseline plasma nicotine metabolite ratio. Following overnight abstinence, smokers received saline followed by escalating intravenous doses of nicotine (7 and 14 mcg/kg) given 30 min apart. Smokers in the first quartile (slower metabolizers) had lower FTND scores, suggesting lower levels of dependence. In contrast, smokers in the fourth quartile (faster metabolizers) reported greater craving for cigarettes following overnight abstinence from smoking and reported greater ratings of nicotine-induced good drug effects, drug liking, and wanting more drug. Higher nicotine metabolite ratio was also associated with greater heart rate increases in response to nicotine. These results suggest that nicotine metabolite ratio may influence the subjective rewarding and physiological effects from nicotine and withdrawal severity.

**Figure 2. Subjective ratings of the pleasurable and aversive effects of intravenous nicotine in smokers.** Shown is the mean value ( $\pm$  SEM) for 6 post-infusion ratings of drug effects for subjects ( $n=26$ ). The subjective ratings for nicotine are relative to the ratings for saline, using the DEQ with a scale of 0-10.

Further, all nicotine doses

In summary, our previous work demonstrates the feasibility of IV nicotine self-administration to determine the reinforcement threshold for nicotine in LITS. Our findings point to a range of nicotine doses, 1.5 to 6.0 mcg/kg, that is well-tolerated by non-dependent smokers and can be used to determine the reinforcement threshold. Our group has unique expertise and a track record in conducting IV nicotine administration studies in both male and female smokers.

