Sampling: In each of the five test sessions, subjects will be randomly assigned to one of the five doses of nicotine: 0.0125, 0.025, 0.05, 0.1 and 0.2 mg/70 kg. Subjects will first receive saline and the assigned nicotine dose in a randomized order and double-blind fashion. Subjects will be informed that they will be receiving drug A or B, which may be nicotine or saline. This procedure will allow subjects to sample the nicotine and saline that will be available during that session. In addition, subjective and physiological responses to the sample nicotine dose and saline will be assessed.

Nicotine Choice procedure: Beginning 15 minutes after the sampling phase is completed, subjects will be asked to make a choice between drug A or B every 15 minutes for a total of ten choices over 150 minutes. The drug chosen by the subjects will be immediately delivered with the infusion pump over 30 sec in 5 ml of saline. This choice procedure has been used in our IV nicotine self-administration study as well as in many previous studies with various drugs of abuse (Sofuoglu et al. 1999, 2000, 2001; 2009c). One particular advantage of this model, compared to the ad lib models used in previous IV nicotine self-administration studies (Harvey et al. 2004; Rose et al. 2003), is the ability to control amount of nicotine delivered without interfering with the self-administration behavior.

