## **12. Data analysis methods:**

Data analyses: The primary analyses will be intent-to-treat and will include all available data on subjects who complete at least one test day. Mixed-effects models will be used to test the study hypotheses. These models allow for different numbers of observations per subject, use all available data on each subject, and are unaffected by randomly missing data. They also provide flexibility in modeling the correlation structure of the data. All data will be checked for normality and transformations will be applied as necessary. Significance level of 0.05 will be used for the main hypotheses and Bonferroni correction will be applied for post-hoc tests and secondary analyses.

Specific Aim #1: Aim #1: To assess the threshold reinforcing dose and dose-effect curve for IV NSA at low doses in young adult LITS. Hypothesis #1A: The threshold reinforcing doses for IV NSA will be between 0.0125 to 0.05 mg/70 kg. Hypothesis #1B: The dose-effect curve for NSA will differ between males and females with relatively flat curve in female smokers.

**Aim #1 Analysis:** The reinforcing effects of nicotine will be determined by the number of IV NSAs in each session, ranging from 0 to 10. The threshold dose for NSA will be determined by the lowest dose of nicotine for which the number of NSAs is significantly greater than those for placebo (saline) (i.e., proportion of NSA significantly higher than 0.5). For assessing the dose-response relationship, the parameters of interest will be the slope and shape of the dose-response curve. The slope indicates the degree to which self-administration changes with an increase in nicotine dose (in other words, sensitivity of NSA to changes in nicotine dose).

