**Rationale for sample size:** Power for Specific Aims 1 and 2 is based on our preliminary studies comparing nicotine doses of 0.1, 0.2, 0.3 and 0.4mg to saline (34). We consider a difference between 50% (half of infusions in favor of nicotine) and 67% (two-thirds in favor of nicotine) as clinically meaningful. With our sample of 72 subjects we can detect such a proportion (67%) as statistically different from 50% with 80% power assuming two-sided test and alpha=0.05 (Specific Aim 1). Also with our sample of 72 subjects, we can detect medium effects ( $d'=0.34$ ) for the threshold tests on “good effects” and “drug liking” under the same assumptions (Specific Aim 2).

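### The Aim 2A comparison tests DEQ ratings against 0 with no saline reference, so a dose that feels like saline can be declared above threshold

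*Combined protocol and SAP*

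**What the plan says.** Section 12, Aim 2 Analysis, takes as dependent variables two positive items (liking, wanting more) and two negative items (disliking, lightheaded or dizzy). It describes the positive ones as "items of the Drug Effects Questionnaire, ranging from 0 to 100". Aim 2A is to be analysed along the lines of Aim 1A, with a linear random-effects model because the outcomes are continuous. The only reference value then given is: "Furthermore, the mean ratings at each dose will be compared to 0". The Aim 2 analysis text does not mention saline, a difference score or a saline level of the dose factor.

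Elsewhere the reference is saline:

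- **Section 12, Aim #1 Analysis:** the threshold is the lowest dose at which "the number of NSAs is significantly greater than those for placebo (saline").
- **Section 12, Rationale for sample size:** power for both aims rests on pilot work "comparing nicotine doses of 0.1, 0.2, 0.3 and 0.4mg to saline".
- **Section 5, Preliminary Studies, Study 1:** the pilot result reads "The aversive effects were significantly higher relative to saline in response to nicotine at 0.3 mg".
- **Section 5, Figure 2 caption:** "The subjective ratings for nicotine are relative to the ratings for saline".

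Saline ratings will be available. Section 11.E, under Sampling, says that "subjective and physiological responses to the sample nicotine dose and saline will be assessed".

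**The concern.** Aim 1A needs no separate placebo term. Every choice is nicotine or saline, so a choice proportion of 0.5 is itself the placebo comparison. A rating on a 0 to 100 scale has no such built-in control. It cannot be negative, so its mean is 0 only if every subject rates 0. Subjects are told that each infusion may be nicotine or saline, so some non-zero ratings after saline are plausible. A test of the raw mean against 0 can then reject for a dose that feels exactly like saline.

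Hypothesis 2A concerns where two thresholds fall: the positive one between 0.0125 and 0.1 mg/70 kg, the negative/aversive one at 0.1 mg/70 kg or higher. If saline ratings are not all 0, the raw comparison moves both towards 0.0125. That could confirm the positive part and refute the aversive part with no true nicotine effect on either.

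**Working it through.** **Inputs from the documents.** n = 72, two-sided alpha 0.05, 80% power and detectable d' = 0.34 (Rationale for sample size); raw scale 0 to 100 and reference value 0 (Aim 2 Analysis); five doses, three of them below 0.1 mg/70 kg (0.0125, 0.025, 0.05).

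**Not in the documents.** The mean, SD and share of non-zero ratings after saline. These are assumed below and varied.

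**Step 1: reproduce the plan's figure.** For a single mean or a paired difference:

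- Normal approximation: d = (z0.975 + z0.80)/√72 = (1.960 + 0.842)/8.485 = 0.330.
- Noncentral t, 71 df: d = 0.335.

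The stated 0.34 is reproduced. The same formula serves a raw mean against 0 and a paired nicotine-minus-saline difference against 0, so the figure does not show which was intended.

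**Step 2: false-pass rate, normal theory.** Suppose a dose has the same rating distribution as saline, with mean m and SD s. The raw t test rejects upwards with probability P(T > t0.975,71), where T is noncentral t with noncentrality (m/s)√72.

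| Saline mean | SD 10 | SD 15 | SD 20 |
|---|---|---|---|
| 0 | 2.5% | 2.5% | 2.5% |
| 2 | 39% | 20% | 13% |
| 3 | 71% | 39% | 24% |
| 5 | 99% | 80% | 55% |
| 10 | 100% | 100% | 99% |

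**Step 3: zero-heavy ratings.** A share p of subjects gives an exponential rating (mean 10 or 20, capped at 100) and the rest give 0. Ignoring the cap, mean/SD = √(p/(2 − p)), whatever the exponential mean: 0.16, 0.23, 0.28, 0.33 and 0.42 for p = 5, 10, 15, 20 and 30%. Simulated values agree to within 0.01.

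Put differently, if k of 72 subjects give a non-zero rating, t is roughly √(k/(2 − k/72)). Setting this to the critical value 1.994 gives k of about 7.5; at alpha 0.01 (critical value 2.647) it gives about 12.8. So about 8 of 72 subjects reporting anything is enough at alpha 0.05, and about 13 at alpha 0.01.

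Results from 20,000 simulated trials per scenario, nicotine and saline identically distributed, upper-tail rejections of a two-sided test:

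| Share rating above 0 | Raw vs 0, alpha 0.05 | Raw vs 0, alpha 0.01 |
|---|---|---|
| 5% | 12% | 0.2–0.3% |
| 10% | 59% | 10% |
| 15% | 89% | 42% |
| 20% | 98% | 75% |
| 30% | about 100% | 98% |

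The paired nicotine-minus-saline test at alpha 0.05 passes in 0.3–2.4% per dose across these scenarios. Alpha 0.01 is Bonferroni over five doses (0.05/5). The plan says "Bonferroni correction will be applied for post-hoc tests and secondary analyses" but does not say whether these per-dose tests fall under it.

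**Step 4: effect on the aversive threshold.** The chance that at least one of the three doses below 0.1 passes, which would wrongly place the threshold below 0.1 (exponential mean 20, 4,000 trials; the range runs from the same people to independent people being the non-zero raters across sessions):

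| Share rating above 0 | Alpha 0.05 | Alpha 0.01 |
|---|---|---|
| 5% | 22–31% | under 1% |
| 10% | 77–94% | 19–28% |
| 15% | 97–100% | 63–81% |
| 20% | about 100% | 91–98% |

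With the paired saline difference at alpha 0.05 the corresponding figure is 1–7%.

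**The case against.** The strongest reply is that a saline-adjusted analysis was meant. The sentence on 0 begins as an addition and is not labelled the threshold test. The analysis is modelled on Aim 1A, whose threshold is against placebo. The pilot figure shows ratings relative to saline, for which 0 is the natural null, and the power paragraph cites a comparison with saline. This is a fair reading of intent. It does not rescue the text: a difference score would not be confined to 0 to 100, no saline term appears, and 0 is the only reference value given for Aim 2A. If a saline-corrected rating was intended, the plan must say so.

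The second reply is that the percentages rest on assumed inputs and a one-sample t test on one rating per subject, whereas the plan has a random-effects model, possible transformations and several ratings after each infusion. That stands. The figures illustrate the mechanism and do not estimate this trial's error rate. If nearly all saline ratings are 0 there is little or no harm: with 2% non-zero raters the raw test passes in about 0.5% of trials.

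Two smaller points also stand. The power statement names only positive effects, so the aversive threshold has none. And because the two samples are 15 minutes apart in random order, saline sometimes follows nicotine. Randomised order keeps the difference usable, but carryover could dilute it, so an order term is sensible.

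**Conclusion.** The concern holds. Followed as written, the rule tests whether subjects report any effect, not whether nicotine differs from saline, so it is the wrong comparison for a threshold and not merely a missing detail. At n = 72 the error is negligible if almost nobody rates saline above 0. At alpha 0.05 it becomes large once about 10% do (59% per dose); Bonferroni over five doses reduces it without removing it (10% per dose at 10% non-zero raters, 42% at 15%). These sizes depend on the assumed rating distribution.

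The reach is limited. Aim 2A has its own hypothesis but is not one of the named main outcomes. Aim 1, the dose slope and Aim 2B make no comparison with 0. The point should be fixed before analysis; it does not threaten the main result.

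**What to change.** In Section 12, Aim 2 Analysis, do one of the following:

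- Define the Aim 2A outcome as the rating after the nicotine sample minus the rating after the saline sample in the same session, at matched time points, and test its mean against 0 at each dose.
- Include saline as the reference level of the dose factor in the mixed model and test each dose against it.

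In either case, name the post-infusion time point or summary used, consider a term for sample order, and state the alpha for the per-dose tests.

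**Cost.** For items on the DEQ form this is wording only, since ratings after the saline sample are already planned, and n need not change. The stated d' = 0.34 carries over only if expressed in SDs of the paired difference (0.335 at alpha 0.05; 0.412 at alpha 0.01).

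One reconciliation is needed first. Section 11.C, Session Measures, lists five DEQ items, and of the four items in the Aim 2 analysis only liking is among them. The documents therefore do not establish that wanting more, disliking and lightheaded/dizzy are collected. The two lists must be brought into agreement.
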